6.1 Data confidentiality

Paper-based records will be kept in a secure location and only be accessible to personnel involved in the study. Computer-based files will only be made available to personnel involved in the study through the use of access privileges and passwords. Wherever feasible, identifiers will be removed from study-related information. Precautions are in place to ensure the data are secure by using passwords and encryption, because the research involves web-based surveys.

6.2 Subject confidentiality

Research material will be obtained from participant surveys and wearable devices. All participants will provide informed consent for access to these materials. The data to be collected include data on participant characteristics and behaviors and step counts. Research material that is obtained will be used for research purposes only. The same procedure used for the analysis of automated data sources to ensure protection of patient information will be used for the survey data, in that patient identifiers will be used only for linkage purposes or to contact patients. The study identification number, and not other identifying information, will be used on all data collection instruments. All study staff will be reminded to appreciate the confidential nature of the data collected and contained in these databases. The Penn Medicine Academic Computing Services (PMACS) will be the hub for the hardware and database infrastructure that will support the project and is where the Way to Health web portal is based. The PMACS is a joint effort of the University of Pennsylvania's Abramson Cancer Center, the Cardiovascular Institute, the Department of Pathology, and the Leonard Davis Institute. The PMACS provides a secure computing environment for a large volume of highly sensitive data, including clinical, genetic, socioeconomic, and financial information. Among the IT projects currently managed by PMACS are: (1) the capture and organization of complex, longitudinal clinical data via web and clinical applications portals from cancer patients enrolled in clinical trials; (2) the integration of genetic array databases and clinical data obtained from patients with cardiovascular disease; (3) computational biology and cytometry database management and analyses; (4) economic and health policy research using Medicare claims from over 40 million Medicare beneficiaries. PMACS requires all users of data or applications on PMACS servers to complete a PMACS-

hosted cybersecurity awareness course annually, which stresses federal data security policies under data use agreements with the university. The curriculum includes Health Insurance Portability and Accountability Act (HIPAA) training and covers secure data transfer, passwords, computer security habits and knowledge of what constitutes misuse or inappropriate use of the server. We will implement multiple, redundant protective measures to guarantee the privacy and security of the participant data. All investigators and research staff with direct access to the identifiable data will be required to undergo annual responsible conduct of research, cybersecurity, and HIPAA certification in accordance with University of Pennsylvania 334 regulations. Data will be stored, managed, and analyzed on a secure, encrypted server behind the University of Pennsylvania Health System (UPHS) firewall. This server was created for projects conducted by the Penn Medicine Nudge Unit related to physician and patient behavior at UPHS. All study personnel that will use this data are listed on the IRB application and have completed training in HIPAA standards and the CITI human subjects research. Data access will be password protected. Whenever possible, data will be deidentified for analysis.

6.3 Subject privacy

Interested participants will be directed to the Way to Health portal where they will be asked to enter data related to eligibility and their demographic characteristics. Enrollment will include a description of the voluntary nature of participation, the study procedures, risks and potential benefits in detail. The enrollment procedure will provide the opportunity for potential participants to ask questions and review the consent form information prior to making a decision to participate. Participants will be told that they do not have to answer any questions if they do not wish and can drop out of the study at any time, without affecting their medical care or the cost of their care. They will be told that they may or may not benefit directly from the study and that all information will be kept strictly confidential, except as required by law. Subjects will have access to a copy of the consent document. All efforts will be made by study staff to ensure subject privacy.

6.4 Data disclosure

The following entities, besides the members of the research team, may receive protected health information (PHI) for this research study: Wells Fargo, the company which processes study related payments. Patient addresses and account balances will be stored on their secure computers. Fitbit, the company that designs and manufactures the wearable devices used in the study to track participant physical activity. Twilio, Inc., the company which processes some 359 study-related messages. Twilio will store patients' phone numbers on their secure computers. Qualtrics, Inc., the company which processes most study-related surveys. Qualtrics will house de-identified answers to these surveys on their secure servers. The Office of Human Research Protections at the University of Pennsylvania -Federal and state agencies (for example, the Department of Health and Human Services, the National Institutes of Health, and/or the Office 364 for Human Research Protections), or other domestic or foreign government bodies if required by 365 law and/or necessary for oversight purposes.

6.5 Data safety and monitoring

The Principal Investigator will be responsible for monitoring the study. All participants will be given anticipatory guidance on when to seek medical attention. In addition, participants will be asked to report to the study team any injuries or medical care that they feel resulted from

participation in the study. They can either call the study team or send an email. The research coordinator will call the participant to collect information regarding the issue and then the PI will review and determine whether it is ok to proceed, further investigation is needed, or the participant should stop the study. For this study there will be no stopping rules or endpoints and thus no planned interim analyses.

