3.1. General Overview

The GAME PAD study is a two-arm randomized controlled trial aimed at evaluating whether a home-based walking program with automated coaching augmented with gamification and behavioral economic principles improves functional capacity in patients with PAD. The study will randomize 100 patients with PAD to a 16-week home-based walking program using goal-setting alone (attention control) or to the same home-based walking program with automated coaching augmented with gamification and behavioral economic principles. There will be a 2-week run-in period to obtain baseline measures of physical activity, followed by a 16-week intervention period, and an 8-week follow-up period (see study protocol figure below).

The study will be conducted using Way to Health, a research information technology platform at the University of Pennsylvania used previously for physical activity behavioral interventions.

After institutional review board (IRB) approval of the study, patients who meet the eligibility criteria will be contacted by email, phone call or letter to invite them to participate. Those who

qualify and express interest will provide online informed consent to the study procedures. All patients will receive a wearable activity tracker (Fitbit Inspire) that will be enrolled in the Way to Health platform. The Fitbit and Way to Health platform will continuously track patients' steps and survey patients regarding pain with walking monthly. Within the Way to Health platform, patients will be randomized to one home-based exercise program or the other. All other management decisions are completely at the discretion of the care providers. Data capture will include:

- **Baseline case report form** (for each patient) collecting clinical information abstracted from the medical record
- **Patient-reported quality of life and functional limitation related to PAD** collected via telephone survey and/or the Way to Health platform at the time of enrollment and at 16- and 24-week follow-up
- **Psychometric features** collected via in-person survey at the time of enrollment
- **Daily step count** and calculated **exercise minutes** collected via FitBit charge
- **Patient-reported pain with ambulation** collected via the Way to Health platform at monthly intervals

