4) Supportive sponsor: Each participant will select a family member or friend of their choice who will serve as a supportive sponsor. This person will receive a weekly email with the participant's progress including accumulated points, level in the game, and average step count. This supportive sponsor will help to enhance social incentives to motivate the individual towards his or her goal. We will encourage participants to select someone with whom he or she comes into frequent contact and is close to such as a partner, family member, or friend that they see often. Prior to starting in the study, we will conduct a three-way phone call with the participant and their supportive sponsor. We will provide an overview of study procedures for their arm assignment, and then prompt the participant and supportive sponsor to discuss ways in which they can help the participant meet their step goals. At least 3 goals will be decided upon during the conversation, and if needed, we will provide suggestions for supporting the participant. The goals that are decided upon will be entered into a survey by study staff, and will be included in weekly emails to the supportive sponsor. After 8 weeks, we will reach out to the participant and supportive sponsor if the participant is stuck in lower levels of blue or bronze to determine if changes should be made to the original support goals. Participants without a supportive sponsor will not be excluded from study participation, and will complete a slightly modified version of the baseline and 8-week phone call, if necessary, in two-way conversations with study staff.

The intervention will end after 16 weeks, but participants will continue to receive a daily text message stating whether they achieved their step goal on the prior day during the 8 week follow-up period.

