4.6. End-of-Study Questionnaire Completion

At the end of the 16-week intervention, patients will be alerted by the Way to Health platform to return to the website to complete an end-of-study questionnaire consisting of the San Diego Claudication Questionnaire, the Walking Impairment Questionnaire, the Patient-Reported Outcomes Measurement Information System (PROMIS) measures of mobility, pain interference, and satisfaction with social roles and activities, and the SF-36 physical functioning scale. Patients will complete the same questionnaire again 8 weeks later.

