6.6 Risk/benefit

6.6.1 Potential study risks

The program will use a gradual increase in physical activity during the first month that should pose little health risk to participants. Participants are given guidance on when to seek medical attention and a reporting protocol is in place to capture any changes in symptoms with physical activity. Another potential risk of this study is a breach of participant confidentiality. We will minimize this risk by using secure data methods as described previously. Due to the financial incentives in this study, we will be collecting social security numbers so that we can complete W-9 forms for participants. Social security numbers only will be used to generate W-9 forms and will be deleted once they are no longer needed. We will also collect home addresses to mail incentive payments. This will be done through a University of Pennsylvania approved partnership with Wells Fargo. Accidental disclosure of social security numbers could lead to identity theft. We will use commercial-grade encryption to protect social security information in transit. Names and addresses will be stored in encrypted databases. These data will be viewable only by the respective participants, the study coordinator(s) and the project manager(s). All other members of the research team will be able to view only participant ID numbers. Even the study arms will be identified by code letters until both the statistician and PI agree that analysis is complete.

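### Injuries and medical care are recorded only when a participant attributes them to the study and makes contact; no scheduled question asked regardless of cause is described in either arm

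*Combined protocol and SAP*

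**What the plan says.** Section 6.5 is the only place that describes how injuries and medical care reach the study team. All participants get guidance on when to seek care, and "participants will be asked to report to the study team any injuries or medical care that they feel resulted from" their participation. The route is theirs to start: "They can either call the study team or send an email". Staff act after that: "The research coordinator will call the participant to collect information regarding the issue", and the principal investigator then reviews the case.

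Section 6.6.1 is broader. It says that "a reporting protocol is in place to capture any changes in symptoms with physical activity", but names no instrument or schedule.

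Some information on symptoms is solicited from everyone. Under Section 3.1 the platform will "survey patients regarding pain with walking monthly". Under Section 4.6 participants "return to the website to complete an end-of-study questionnaire consisting of the San Diego Claudication Questionnaire", together with walking, PROMIS and SF-36 scales, at week 16 and again eight weeks later. Neither section lists a question about injuries or medical care.

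Staff contact after allocation is described only for the intervention arm (4.5.2): a call before the programme starts, and a contact after 8 weeks for participants stuck at blue or bronze. Section 4.5.1 describes the control arm as receiving daily automated texts. Section 5 lists no harms outcome and no tabulation of harms.

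**The concern.** An injury or an episode of care must pass two filters before it is recorded: the participant must link it to the study, and must then decide to get in touch. The first filter is a weak one in this population. People with PAD have a ready alternative explanation for a fall, a hospital visit or an unplanned procedure, and may never connect it with a walking programme.

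Little else in the plan would recover what is missed. Trial participation is managed virtually, clinical staff at the sites take no part in research procedures (3.2), and abstraction from the medical record is described only for the baseline form (3.1).

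Two things are at stake. Monitoring by the principal investigator would rest on an incomplete list of events. Any later statement about safety by arm would also rest on counts whose completeness is unknown and may not be equal, since participants cannot be blind to the programme they follow and one arm has a staff contact that the other lacks.

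**Working it through.** The plan states no event rate, expected harm count or capture rate, so there is no figure to reproduce. The check is a comparison of the text, followed by an illustration of what can and cannot be inferred.

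**1. Sources of information, by type of event**

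| Source | Arms | Solicited? | Needs attribution to the study? | Injuries or medical care asked about? |
|---|---|---|---|---|
| Call or email (6.5) | both | no | yes | yes |
| Monthly walking-pain survey (3.1) | both | yes | no | none described |
| Week-16 and week-24 questionnaires (4.6) | both | yes | no | none listed |
| Week-8 contact (4.5.2) | intervention, if at blue or bronze | yes | not applicable | none stated; purpose is level reset, step goal and support goals |

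For injuries and medical care, the only row that asks about them is the one that needs both attribution and initiative. For leg symptoms, the second and third rows work in both arms without attribution. However, the plan does not say that those answers are reviewed for safety, and Section 5 names no analysis of the monthly pain answers.

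**2. Effect of the filters on counts**

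Expected recorded events per arm = n × p × c, where n is the arm size, p the true risk, and c = P(participant attributes the event) × P(participant makes contact, given attribution). The plan gives n = 50 (5.2). Both p and c are assumptions, for illustration only.

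- True events: 50 × 0.10 = 5 up to 50 × 0.30 = 15 per arm, the same in both arms.
- Equal capture of 30%: 5 × 0.30 = 1.5 up to 15 × 0.30 = 4.5 recorded per arm. The ratio is 1.0, but 70% of events are lost.
- Capture of 30% in control and 50% in intervention: 1.5 v 2.5 up to 4.5 v 7.5. The apparent risk ratio is 0.50 / 0.30 = 1.67.
- Capture of 50% in control and 70% in intervention: the ratio is 0.70 / 0.50 = 1.40.
- Capture of 50% in control and 30% in intervention: 2.5 v 1.5 up to 7.5 v 4.5. The ratio is 0.30 / 0.50 = 0.60.

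The loss of events needs no difference between arms. A spurious or hidden difference does.

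**3. Can the direction be settled from the text?**

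No. If the week-8 contact brought events to light, capture would be higher in the intervention arm. The participants it reaches are those missing step goals, and illness or injury is a plausible reason for that. Attribution could go either way. A participant who is pressed to walk more may link a fall to the study more readily, whereas one who is repeatedly told by text that walking helps PAD (4.5.2) may do so less readily. All of this is inference.

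**The case against.** The case for leaving the plan alone has real substance. Walking pain and symptom scales are already collected from everyone without any attribution. The call-or-email route, coordinator follow-up and review by the principal investigator apply equally to both arms. Sections 6.5 and 6.6.1 can be read together, one covering injuries and care and the other symptom changes, with the monthly survey serving the second. No comparison of harms by arm is planned, and reporting by the participant can be defended as proportionate in a walking trial that the protocol regards as low risk (6.6.3). An open question about any medical care would also pick up much routine care.

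Most of this stands, and it rules out three stronger readings that a reader might infer.

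- *That all harms depend on volunteering and attribution.* This is not so for leg symptoms (3.1, 4.6). It holds for injuries and medical care.
- *That the introductory call in the intervention arm adds to event detection.* The text places it before the programme begins: "Prior to starting in the study, we will conduct a three-way phone call with the participant and their supportive sponsor". It cannot reveal events from the intervention period. Only the week-8 contact can, and it is conditional and has no stated question on harms.
- *That harms will be counted unequally, in a known direction or by a known factor.* No rate in the documents supports this. The figures above only show that the ratio can move either way.

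The objection does not remove the gap itself. No scheduled question on injuries or medical care is described for anyone. The absence of a planned comparison by arm limits the damage, but it does not make the monitoring list complete. The worry about routine care is met by asking about unplanned care.

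**Conclusion.** The point holds in a limited form. As written, the plan would under-record injuries and medical care in both arms, because each event must be both attributed to the study and volunteered. Capture may differ between arms, but that is a possibility and not a demonstrated bias. The size of the under-count, and the size and direction of any difference, cannot be derived from the documents.

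The wording of 6.6.1 is a smaller matter: it needs to name its instrument so that it agrees with 6.5. The primary step-count outcome and its analysis are not affected. This is a cheap improvement to safety monitoring and reporting, not a flaw that undermines the trial.

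The conclusion assumes that the protocol describes all the harm-collection procedures. If the reporting protocol mentioned in 6.6.1 is a separate document with a scheduled question on injuries and care, all that remains is to cite it and to plan a tabulation.

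**What to change.** - Add one identical item, in both arms, to the monthly Way to Health survey and to the 16- and 24-week surveys: any fall, injury or unplanned medical care since the last survey, regardless of what the participant thinks caused it. Keep the call-or-email route in 6.5 alongside it.
- Add to Section 5 a descriptive tabulation of the responses by arm, with the number who answered each survey. No test is needed.
- Record separately any event learned during intervention-arm staff contacts, so that the by-arm table rests on the source common to both arms.
- State in 6.6.1 which instrument captures symptom changes, for example the monthly pain survey, and reconcile that sentence with 6.5.

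The cost is a protocol amendment, a short extra item per survey and some coordinator follow-up of positive answers, part of it for events unrelated to walking. No new visits are needed and neither programme changes. The item will still miss events in people who do not answer, which is why the table should show completion by arm.

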6.6 Risk/benefit

6.6.1 Potential study risks

The program will use a gradual increase in physical activity during the first month that should pose little health risk to participants. Participants are given guidance on when to seek medical attention and a reporting protocol is in place to capture any changes in symptoms with physical activity. Another potential risk of this study is a breach of participant confidentiality. We will minimize this risk by using secure data methods as described previously. Due to the financial incentives in this study, we will be collecting social security numbers so that we can complete W-9 forms for participants. Social security numbers only will be used to generate W-9 forms and will be deleted once they are no longer needed. We will also collect home addresses to mail incentive payments. This will be done through a University of Pennsylvania approved partnership with Wells Fargo. Accidental disclosure of social security numbers could lead to identity theft. We will use commercial-grade encryption to protect social security information in transit. Names and addresses will be stored in encrypted databases. These data will be viewable only by the respective participants, the study coordinator(s) and the project manager(s). All other members of the research team will be able to view only participant ID numbers. Even the study arms will be identified by code letters until both the statistician and PI agree that analysis is complete.

6.6.2 Potential study benefits

Through participation in this study, each participant will have the potential to increase physical activity which could improve their health and reduce their risk for future disease. If this approach is effective, it could have tremendous benefits for society if adopted on a wide scale to help individuals. It is expected that other people will gain knowledge from this study and that participation could help understand how to effectively motivate individuals to change behavior. Participants may also receive no benefit from their participation in the study.

